### Screening Visits

The ICF will be signed at Screening Visit 1. Subjects will need to sign the ICF prior to any Screening Visit 1 procedures. The Screening period starts at the time the ICF is signed and will be up to 8 weeks in duration. Two Screening visits must be performed within 8 weeks prior to dosing (Baseline Visit/Day 1). There must be a minimum of 4 days between the 2 Screening Visits and a minimum of 4 days (based on last ESA use) between Screening Visit 2 or last retest and the Baseline Visit.

The investigator will maintain a log of subjects and indicate who of the Screened subjects were enrolled or excluded and the reason for exclusion.

After obtaining informed consent, subjects will undergo a number of screening activities.

Two Hb values, at least 4 days apart, measured by the central laboratory during Screening must be between 8.0 and 11.0 g/dL (inclusive) in the US or between 9.0 and 12.0 g/dL (inclusive) in Europe to qualify for inclusion into the trial. If the subject’s Hb does not qualify after Screening Visit 1, Screening Visit 2, or retest Hb, the subject should be considered a Screen failure. Refer to [Section 5.4.1](#) for further details regarding repeating laboratory measurements during the Screening period.

For all subjects, it is recommended that no additional ESA doses be administered after Screening Visit 2 and prior to the Baseline Visit (Day 1).

For all subjects, it is required that a minimum period as outlined below be observed between the last dose of ESA administered during Screening and Randomization Visit:

- 2 days after last dose of epoetin analogues.

- 7 days after last dose of darbepoetin alfa.
- 14 days after last dose of methoxy polyethylene glycol-epoetin beta.

After discussion with the Medical Monitor, screening may be extended for an additional 2 to 4 weeks based on the subject's Hb level or Hb trajectory or based on timing of the last ESA dose given during screening.

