For all subjects, it is recommended that no additional ESA doses be administered after Screening Visit 2 and prior to the Baseline Visit (Day 1).

For all subjects, it is required that a minimum period as outlined below be observed between the last dose of ESA administered during Screening and Randomization Visit:

- 2 days after last dose of epoetin analogues.
- 7 days after last dose of darbopoetin alfa.

- 14 days after last dose of methoxy polyethylene glycol-epoetin beta.

After discussion with the Medical Monitor, screening may be extended for an additional 2 to 4 weeks based on the subject's Hb level or Hb trajectory or based on timing of the last ESA dose given during screening.

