## **5.4 Screen Failures**

A screen failure is a subject from whom informed consent is obtained and is documented in writing (ie, subject signs an informed consent form [ICF]), but who is not randomized or assigned trial treatment.

If the subject meets the definition of a screen failure in this trial, the following information (at a minimum) will be recorded in the eCRF:

- Date of informed consent.
- Visit date (Screening Visit).
- Demographics (collection date, birth date, sex, race, ethnicity, country).
- Result of eligibility assessment.
- Screen failure date.
- Reason for screen failure.

Investigators must account for all subjects who sign informed consent and will maintain a log of subjects screened and indicate who was randomized or excluded. If the subject is found not to be eligible for randomization, the reason(s) for ineligibility must be documented by the investigator.

Screening numbers assigned to subjects who fail Screening will not be reused.

Subjects who fail to qualify for the trial at the initial Screening Visit will receive a new subject number for each rescreening attempt (see [Section 5.4.1](#)). If rescreened, the subject will also sign a new ICF and will repeat all Screening procedures.

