### **5.4.1 Retesting and Rescreening**

Subjects who initially fail to qualify for the trial based on laboratory test results may have any individual laboratory parameter retested 1 time within the 8-week Screening period at the discretion of the investigator. Retesting within the 8-week Screening period does not constitute rescreening; however, if retesting falls outside of the 8-week Screening period, it should be considered a rescreen. All screening laboratories, including any repeat measurements, must be performed within the 8-week Screening window with a minimum of 4 days between the last qualifying repeat measurement and the Baseline Visit.

Subjects who fail to qualify for the trial based on laboratory tests may be considered for rescreening at the discretion of the investigator if it is considered that the subject status has changed, and the subject may now qualify for the trial. Each screening attempt

includes the potential of a retest. Additionally, subjects who fail to qualify for the trial based on inclusion criteria values for TSAT, ferritin, folate, or B12 values may be considered for rescreening after receiving replacement therapy. A minimum of 3 weeks from IV iron replacement therapy (for low TSAT and ferritin values) must be observed prior to collecting next trial visit Hb value.

Screening is limited to 3 attempts (initial Screening and 2 additional rescreening attempts). A new informed consent is required to be signed prior to every rescreening.

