### **Baseline Visit (Day 1)**

The Baseline Visit must be performed after a minimum period as outlined above. Subject will take their first dose of IMP at the investigative site during the Baseline Visit.

Iron supplementation as needed to maintain ferritin  $\geq$  100 ng/mL or TSAT  $\geq$  20% (per local product label; see [Section 6.5.2.1](#)). Subjects will be instructed to take vadadustat at least 1 hour before oral medications containing iron. AEs should be assessed after receiving the first dose of IMP.

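### The only scheduled pregnancy test has no age limit at the first dose: it can be up to 52 days old, or 66 to 80 days if an extension of screening moves the 8-week limit

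*Protocol*

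**What the plan says.** **Pregnancy testing.** The Schedule of Assessments (Protocol 1.3) has one entry in the pregnancy-test row, at Screening Visit 2. Footnote [e] makes this a serum test and excludes a woman who tests positive. On further serum or urine tests, the footnote says they should be done and Section 8.7.1 says they may be. Both leave the number to the investigator or local regulation, and neither names a date. Section 8.7.1 requires results to be in hand and negative before the first dose, with no maximum age. Appendix 3 (10.3) asks only for a test at screening. On Day 1, Section 8 says: "Subject will take their first dose of IMP at the investigative site during the Baseline Visit".

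**Screening timing.** Consent is signed at Screening Visit 1, and "The Screening period starts at the time the ICF is signed and will be up to 8 weeks in duration". Section 8 also requires:
- both visits to fall in the 8 weeks before dosing;
- at least 4 days between the two visits;
- at least 4 days from Visit 2, or the last retest, to Baseline.

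The protocol recommends no ESA dose after Visit 2. It requires 2, 7 or 14 days since the last dose of an epoetin, darbepoetin alfa or methoxy polyethylene glycol-epoetin beta respectively.

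**Extension.** The same section adds: "After discussion with the Medical Monitor, screening may be extended for an additional 2 to 4 weeks". The reasons given are haemoglobin level or trajectory, or the timing of the last ESA dose. The Synopsis repeats this. Section 5.4.1 says "All screening laboratories, including any repeat measurements, must be performed within the 8-week Screening window" and "if retesting falls outside of the 8-week Screening period, it should be considered a rescreen". It does not mention the extension.

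**The concern.** A negative test says nothing about the time after the sample was drawn. A woman who conceives between Screening Visit 2 and Day 1, and has no reason to suspect it, can be dosed while the site has met every testing requirement in the protocol. The longer the permitted interval, the weaker the requirement of a negative result before dosing becomes.

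What is at stake is participant protection. Appendix 3 calls the fetal risk limited on studies to date and reports no teratogenicity in animals. It also reports lower fetal weight and reduced ossification in rats at the top dose, and says that peri-postnatal studies had not been done. The protocol clearly intends to keep pregnant women off drug, but its one fixed test is not tied to the date of dosing.

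The extension adds a second, smaller problem. The text does not say whether the 8-week visit and laboratory limits move with it, so the ceiling on the age of any screening test is unstated exactly where it would be longest.

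**Working it through.** **The plan's own figure.** Section 4.1 and SAP 2.2 give about 64 weeks per subject. 8 (screening) + 52 (treatment) + 4 (follow-up) = 64, so this figure includes no extension. With one it would be 66 to 68 weeks.

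**Inputs** (Protocol 4.1 and Section 8, Screening Visits): screening period 8 × 7 = 56 days from Visit 1; at least 4 days from Visit 1 to Visit 2; at least 4 days from Visit 2 to Day 1; extension 14 to 28 days; ESA intervals 2, 7 and 14 days.

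**Oldest permitted test at the first dose** = longest interval from Visit 1 to Day 1, minus shortest interval from Visit 1 to Visit 2.

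| Case | Visit 1 to Day 1 | Oldest Visit 2 test |
|---|---|---|
| No extension | 56 days | 56 − 4 = 52 days |
| 2-week extension moves the limit | 56 + 14 = 70 days | 70 − 4 = 66 days |
| 4-week extension moves the limit | 56 + 28 = 84 days | 84 − 4 = 80 days |

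The last two rows assume that the extension is used in full and Visit 2 is not repeated. The youngest permitted Visit 2 test is 4 days old.

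**More typical interval.** Assume the last ESA dose is given at Visit 2 and the subject is randomized as soon as allowed. The interval is then the larger of 4 days and the ESA interval:
- epoetin: max(4, 2) = 4 days;
- darbepoetin alfa: max(4, 7) = 7 days;
- methoxy polyethylene glycol-epoetin beta: max(4, 14) = 14 days.

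**Does any other provision fix a test near Day 1?**
- *Negative result before dosing (8.7.1):* sets no age, so the Visit 2 result satisfies it.
- *Extra tests (footnote [e], 8.7.1):* no date, and the number is discretionary.
- *Eligibility review at Baseline (1.3, 10.1.8.2) and the exclusion for a positive test (5.2.2):* without a new test there is no new result to review.
- *Contraception (5.2.2, 10.3):* lowers the chance of conception but does not detect it. Read literally, Appendix 3 also lists a negative screening serum test among the exceptions to using two methods. The exclusion criterion in 5.2.2 has no such exception.
- *Withholding drug (10.3):* needs suspicion of pregnancy.
- *No ESA after Visit 2 (Section 8):* shortens the interval in practice, but is a recommendation. A haemoglobin retest after Visit 2 can lengthen the interval without renewing the pregnancy test.

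**The case against.** The strongest reply is that 52 days is unrealistic. These patients are on maintenance ESA, so a 52-day interval means either 52 days without ESA or setting aside the recommendation. Contraception is required, and the listed methods that carry a start time begin at or before Screening Visit 1 and so cover the interval. Drug is withheld on suspicion, and investigators can add tests. Any particular window, 7 days included, is a matter of choice. All of this stands and keeps the point small. It does not supply a dated test.

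A reader might also infer that the extension contradicts the 8-week rule, so that some sites would dose an extended subject while others would have to rescreen under the rule that "If rescreened, the subject will also sign a new ICF and will repeat all Screening procedures". The documents do not support a claim that strong. A clause allowing screening to be extended reads naturally as an exception to the 8-week period, and a reading that leaves it without effect is not a serious rival. Each extension also requires discussion with the Medical Monitor. The retest rule in 5.4.1 concerns subjects who first fail on a laboratory value, so a qualified subject waiting out an ESA interval has no retest to trigger it. What remains is missing conforming text.

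On liver safety, dosing at Baseline before that day's central-laboratory result is back applies to every subject. An extension adds 14 to 28 days to an accepted 56.

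**Conclusion.** The point holds for the pregnancy test and is minor. One test is scheduled and its age at dosing is not limited. The permitted range is 4 to 52 days without an extension. The ceiling is 66 to 80 days if an extension moves the 8-week limit and Visit 2 is not repeated. It would be wrong to give 52 days as the ceiling in all cases, and equally wrong to read any of these ceilings as typical: 4 to 14 days is more likely under the assumption stated above. The documents give neither the number of women of childbearing potential nor the number of extended subjects, so the number affected cannot be estimated.

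The extension wording is a drafting gap only. Neither matter touches the sample size, randomization, type I error control or any efficacy analysis.

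**What to change.** **Main change.** Add to the Schedule of Assessments and footnote [e], and align Section 8.7.1 and Appendix 3: women of childbearing potential must have a negative pregnancy test drawn within a stated short window before Day 1, with the result available before the first dose. A Visit 2 test inside the window counts.

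The window is a proposal. With 7 days, a Visit 2 test drawn 4 to 7 days before Day 1 suffices, but a woman given methoxy polyethylene glycol-epoetin beta at Visit 2 must wait 14 days and would need a second test. With 14 days her Visit 2 test can count, at the price of an older result.

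**Secondary drafting note.** State in Sections 5.4.1 and 8 that the 8-week visit and laboratory limits move with an approved extension, and that an approved extension is not a rescreen. The sentence in 5.4.1 covering all screening laboratories has to change too; repeating selected tests would not satisfy it. If the limits do move, repeat the screening liver tests when Day 1 falls more than 8 weeks after Screening Visit 1, since Visit 1 values could otherwise be 70 to 84 days old and Section 2.4 lists hepatotoxicity as a confirmed important risk.

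**Cost.** A protocol amendment with ethics approval (10.6), at most one extra pregnancy test at a routine dialysis session for the few women affected and, if the limits move, repeat liver tests for subjects extended past 8 weeks. It helps only subjects not yet dosed.

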### **Baseline Visit (Day 1)**

The Baseline Visit must be performed after a minimum period as outlined above. Subject will take their first dose of IMP at the investigative site during the Baseline Visit.

Iron supplementation as needed to maintain ferritin  $\geq$  100 ng/mL or TSAT  $\geq$  20% (per local product label; see [Section 6.5.2.1](#)). Subjects will be instructed to take vadadustat at least 1 hour before oral medications containing iron. AEs should be assessed after receiving the first dose of IMP.

### **Treatment Period Visits (Week 2 through Week 52)**

Treatment Period Visits will occur from Weeks 2 to 52. The primary efficacy evaluation period will occur from Weeks 20 to 26, and the secondary efficacy evaluation period will occur from Week 46 to 52.

### **End of Treatment Visit/Early Termination Visit**

The EOT Visit will be conducted on Week 52 for subjects that complete the 52-week treatment period ( $\pm$  3 days). For subjects that end treatment prior to Week 52, the ET assessments should be performed within 7 days after stopping IMP.

### **Exit Interview**

Using a semi-structured interview guide, a contributing CRO will conduct a single individual telephone interview with subjects at a subset of sites. The purpose of the exit interview is to document the subject's evaluation of the treatment received as well as their overall experience of the clinical trial. The information obtained during the exit interview will help to gain a better understanding of the both the disease and treatment from the subject's perspective. It is anticipated that each interview will be approximately 60 minutes. All exit interviews will be conducted by the CRO, audio recorded, and transcribed for analysis during the 4-week follow-up period.

A sample size of 60 subjects in the US and up to 30 subjects from Europe is targeted and sufficient to address trial objectives. The sample size was selected based on the subject diversity in the trial population; the minimum sample size required for exit interviews is

20 subjects. Interviews will be conducted using English or translated versions of the interview guide as appropriate.

The interview guide will begin with a very brief overview of the interview process and very general questions intended to get the subjects talking about their experiences associated with anemia due to CKD (the symptoms and impact of anemia) prior to entering the trial, most important or most bothersome aspects of the disease, and expectations of treatment prior to the trial. As the discussion continues, the semi-structured interview will focus on identifying and understanding the breadth and magnitude of subjects' perceived treatment benefits, including general experiences with trial treatment; anticipated or unanticipated benefits, impact of those benefits; impact of treatment on daily life/functioning; how well treatment addresses most important/bothering symptoms; treatment satisfaction and reasons for satisfaction.

### **Follow-up Visit**

The Follow-up Visit will be conducted 4 weeks after the EOT Visit, or 4 weeks after the last dose of IMP for ET.

### **Unscheduled Visits**

Unscheduled assessments may be conducted at any time as medically warranted. At minimum, the following activities/procedures will be performed.

- Adverse Event assessments.
- Major adverse cardiovascular events (MACE) assessment.
- Any other procedures that are medically warranted at the discretion of the investigator.

## **8.1 Subject Reported Outcome Assessments**

### **8.1.1 36-Item Short Form Health-related Quality of Life**

The SF-36v2 HRQOL is a subject-reported survey of subject health status which will be completed within the ePRO application during the dialysis visits, according to the Schedule of Assessments ([Table 1.3-1](#)).

### **8.1.2 Patient Global Impression of Severity Life**

The PGI-S is a global index that is used to rate the severity of disease. It will be completed within the ePRO application during the dialysis visits, according to the Schedule of Assessments ([Table 1.3-1](#)).

### 8.1.3 Patient Global Impression of Change

The PGI-C is a scale that evaluates all aspects of a subject's health and assesses if there has been an improvement or decline in clinical status. It will be completed within the ePRO application during the dialysis visits, according to the Schedule of Assessments ([Table 1.3-1](#)).

### 8.1.4 Functional Assessment of Cancer Therapy-Anemia

The FACT-An is a subject-reported outcome measure which evaluates quality of life concerns related to anemia and fatigue. It will be completed within the ePRO application during the dialysis visits, according to the Schedule of Assessments ([Table 1.3-1](#)).

## 8.2 Pharmacokinetic Assessments

Plasma samples for PK evaluation will be collected only for subjects randomized to vadadustat to analyze for both the parent compound (vadadustat) and its metabolites.

Collection time points are as shown in [Table 8.2-1](#) and [Table 1.3-1](#) (Schedule of Assessments). Vadadustat may be dosed before or after the start of dialysis. The predose sample should be collected as close to the same time as the serum chemistry sample.

Blood samples will be collected and processed according to the Operations/Laboratory Manual. The actual date and time of the PK sample collection will be recorded in the eCRF. Additionally, the time of the dose of IMP will be recorded in the eCRF and the start and stop time of the dialysis session will be recorded in the eCRF.

**Table 8.2-1 Vadadustat Pharmacokinetic Sampling Schema**

[figure not shown]
	Week 12 Dialysis Day
Predose, within 60 minutes	X
0.5 hours $\pm$ 5 minutes (post-dose)	X
1 hour $\pm$ 10 minutes (post-dose)	X
2 hours $\pm$ 10 minutes (post-dose)	X
3 hours $\pm$ 15 minutes (post-dose)	X

After processing into plasma, aliquots will be placed into appropriately labeled tubes and will be placed in a freezer set at  $-70^{\circ}\text{C}$  or  $-20^{\circ}\text{C}$ , unless otherwise instructed in the Operations/Laboratory Manual.

All plasma samples will be shipped to the bioanalytical laboratory for analysis. Information will be provided in the Operations/Laboratory Manual.

### 8.3 Pharmacodynamic Assessments

Blood samples for EPO, reticulocytes, and other iron indices (ferritin, iron, TIBC, and TSAT) analysis will be collected at the times noted in the Schedule of Assessments ([Table 1.3-1](#)). Blood samples will be collected and processed according to the Operations/Laboratory Manual. For all PD sampling, the time of the previous dose of IMP is to be recorded in the eCRF and the timing of administration of IMP and the start and stop time of the dialysis session will be recorded in the eCRF.

## 8.7 Safety Assessments

Details pertaining to the definitions, collection, reporting, and follow-up of AEs are described in [Section 8.8](#). If the evaluations will occur on a hemodialysis day, the clinical evaluations should be completed before dialysis, if applicable.

### 8.7.1 Clinical Laboratory Assessments

Clinical laboratory samples will be collected at the time points described in the Schedule of Assessments ([Table 1.3-1](#)) to perform the clinical laboratory assessments described in [Section 10.2](#).

Samples for laboratory assays will be sent to a central laboratory for analysis. Detailed instructions for the collection, processing, and shipment of laboratory samples will be provided by the central laboratory. If blood is collected on a hemodialysis day, blood draws should be done prior to dialysis, if applicable. The investigator is responsible for reviewing laboratory results for clinical significance.

Blood samples will be collected for the laboratory evaluations listed in [Section 10.2](#) and will be conducted during the course of the trial. For details regarding the timing of these assessments refer to the Schedule of Assessments ([Table 1.3-1](#)).

- **Pregnancy Test:** A serum pregnancy test will be performed according to the Schedule of Assessments ([Table 1.3-1](#)) for females of childbearing potential. Additional serum or local urine (if possible) pregnancy tests may be conducted throughout the trial in sufficient number, as determined by the investigator or required by local regulations,

to establish the absence of pregnancy during the trial. These results must be available and must be negative before the subject takes the first dose of IMP.

### **8.7.2 Medical History, Demographics, and Physical Examination**

Medical history, demographic information, and physical examination (including height) will be collected according to the Schedule of Assessments ([Table 1.3-1](#)). Relevant medical history (with particular emphasis on previous medical conditions that may lead to exclusion) and significant ongoing medical conditions or diseases should be documented. Dialysis events/issues (ie, the common issues that occur in a given dialysis patient such as pruritus, nausea, hypotension) should be recorded as medical history on the appropriate eCRF.

During the Treatment period, an abbreviated physical examination should be performed at the discretion of the investigator, as clinically indicated.

Dry weight will be collected for all subjects according to the Schedule of Assessments ([Table 1.3-1](#)). For subjects on ESA, subjects will be weighed for dosing as per the local standard of care.

